10.1.6. Source Documents

Source documents provide evidence for the existence of the participant and substantiate the integrity of the data collected. Source documents are filed at the investigator's site.

Data reported on the CRF or entered in the eCRF that are transcribed from source documents must be consistent with the source documents or the discrepancies must be explained. The investigator may need to request previous medical records or transfer records, depending on the study. Also, current medical records must be available.

Definition of what constitutes source data can be found in Section [10.1.5](#).

10.1.7. Study and Site Start and Closure

The study start date is the date on which the clinical study will be open for recruitment of participants.

The sponsor designee reserves the right to close the study site or terminate the study at any time for any reason at the sole discretion of the sponsor. Study sites will be closed upon study completion. A study site is considered closed when all required documents and study supplies have been collected and a study-site closure visit has been performed.

The investigator may initiate study-site closure at any time, provided there is reasonable cause and sufficient notice is given in advance of the intended termination.

Reasons for the early closure of a study site by the sponsor or investigator may include but are not limited to:

- Failure of the investigator to comply with the protocol, the requirements of the IRB/IEC or local health authorities, the sponsor's procedures, or GCP guidelines
- Inadequate recruitment of participants by the investigator
- Discontinuation of further study intervention development.

If the study is prematurely terminated or suspended, the sponsor shall promptly inform the investigators, the IECs/IRBs, the regulatory authorities, and any contract research organization(s) used in the study of the reason for termination or suspension, as specified by the applicable regulatory requirements. The investigator shall promptly inform the participant and assures appropriate participant therapy and/or follow-up.

10.1.8. Publication Policy

In accordance with the sponsor's publication policy, the results of this study will be submitted for publication by a peer-reviewed journal if the results are deemed to be of significant medical importance.

10.2. Appendix 2: Clinical Laboratory Tests

The tests detailed below will be performed by the local laboratory.

Protocol-specific requirements for inclusion or exclusion of participants are detailed in Section [5](#) of the protocol.

Additional tests may be performed at any time during the study as determined necessary by the investigator or required by local regulations.

Pregnancy testing will be conducted as detailed in the SoA (Section [1.3](#)).

Investigators must document their review of each laboratory safety report.

Clinical Laboratory Tests

Hematology	Clinical Chemistry
Hematocrit	Sodium
Hemoglobin	Potassium
Erythrocyte count (RBC)	Bicarbonate
Mean cell volume	Chloride
Mean cell hemoglobin	Calcium
Mean cell hemoglobin concentration	Phosphorus/Phosphate
Leukocytes (WBC)	Glucose (fasting)
Platelets	Blood urea nitrogen
Differential WBC (absolute counts and %) of:	Creatinine
Neutrophils	Uric acid
Lymphocytes	Total protein
Monocytes	Albumin
Eosinophils	Total bilirubin ^a
Basophils	Alkaline phosphatase
Urinalysis	Aspartate aminotransferase
Specific gravity	Alanine aminotransferase
pH	Ethanol testing ^b
Protein	Urine drug screen ^b
Glucose	Hepatitis B surface antigen ^c
Ketones	Hepatitis C antibody ^{c,d}
Bilirubin	HIV ^c
Urobilinogen	Serum pregnancy test (all females) ^c
Blood	Urine pregnancy test (all females) ^e
Nitrite	FSH (postmenopausal females only) ^c
Microscopic examination of sediment ^f	

Abbreviations: FSH = follicle-stimulating hormone; HIV = human immunodeficiency virus; RBC = red blood cells; WBC = white blood cells.

Note: Results of these assays will be validated by the local laboratory at the time of testing. Additional tests may be performed or auto-calculated by the laboratory as part of its standard panel that cannot be removed. Some of the above parameters are calculated from measured values. Omission of calculated values will not be considered as a protocol violation.

- ^a Direct and indirect bilirubin will be analyzed if total bilirubin is elevated.
- ^b Performed at screening and admission to the clinical research unit (CRU; Day -1).
- ^c Performed at screening only.
- ^d Participants with a positive hepatitis C antibody test result can have a confirmatory hepatitis C RNA test.
- ^e Performed for all females on admission to CRU (Day -1). A positive urine test will be confirmed with a serum pregnancy test.
- ^f Test only if dipstick result is abnormal.

10.2.1. Blood Sampling Summary

This table summarizes the approximate number of venipunctures and blood volumes for all blood sampling (screening, safety laboratories, and bioanalytical assays) during the study.

Protocol H8H-MC-LAIA Sampling Summary

Purpose	Blood Volume per Sample (mL)	Number of Blood Samples	Total Volume (mL)
Screening tests ^a	19.5	1	19.5
Clinical laboratory tests ^a	12.5	6	75
Pharmacokinetics	2	51 ^b	102
Pharmacogenetics	10	1	10
Total			206.5
Total for clinical purposes			210

a Additional samples may be drawn if needed for safety purposes.

b Includes additional 3 samples, if required.

10.3. Appendix 3: Adverse Events: Definitions and Procedures for Recording, Evaluating, Follow-up, and Reporting

10.3.1. Definition of AE

AE Definition

- An AE is any untoward medical occurrence in a patient or clinical study participant, temporally associated with the use of study intervention, whether or not considered related to the study intervention.
- Note: An AE can therefore be any unfavorable and unintended sign (including an abnormal laboratory finding), symptom, or disease (new or exacerbated) temporally associated with the use of study intervention.

Events Meeting the AE Definition

- Any abnormal laboratory test results (hematology, clinical chemistry, or urinalysis) or other safety assessments (e.g., ECG, radiological scans, vital signs measurements), including those that worsen from baseline, considered clinically significant in the medical and scientific judgment of the investigator (i.e., not related to progression of underlying disease).
- Exacerbation of a chronic or intermittent preexisting condition including either an increase in frequency and/or intensity of the condition.
- New conditions detected or diagnosed after study intervention administration even though it may have been present before the start of the study.
- Signs, symptoms, or the clinical sequelae of a suspected drug-drug interaction.
- Signs, symptoms, or the clinical sequelae of a suspected overdose of either study intervention or a concomitant medication. Overdose per se will not be reported as an AE/SAE unless it is an intentional overdose taken with possible suicidal/self-harming intent. Such overdose should be reported regardless of sequelae.

Events NOT Meeting the AE Definition

- Any clinically significant abnormal laboratory findings or other abnormal safety assessments which are associated with the underlying disease, unless judged by the investigator to be more severe than expected for the participant's condition.
- Medical or surgical procedure (e.g., endoscopy, appendectomy): the condition that leads to the procedure is the AE.
- Situations in which an untoward medical occurrence did not occur (social and/or convenience admission to a hospital).
- Anticipated day-to-day fluctuations of preexisting disease(s) or condition(s) present or detected at the start of the study that do not worsen.

10.3.2. Definition of SAE

If an event is not an AE per definition above, then it cannot be an SAE even if serious conditions are met (e.g., hospitalization for signs/symptoms of the disease under study, death due to progression of disease).

An SAE is defined as any untoward medical occurrence that, at any dose:
a. Results in death
b. Is life-threatening

The term 'life-threatening' in the definition of 'serious' refers to an event in which the participant was at risk of death at the time of the event. It does not refer to an event, which hypothetically might have caused death, if it were more severe.

c. Requires inpatient hospitalization or prolongation of existing hospitalization

 • In general, hospitalization signifies that the participant has been admitted to hospital for observation and/or treatment that would not have been appropriate in the physician's office or outpatient setting. Complications that occur during hospitalization are AEs. If a complication prolongs hospitalization or fulfills any other serious criteria, the event is serious. When in doubt as to whether "hospitalization" occurred or was necessary, the AE should be considered serious. • Hospitalization for elective treatment of a preexisting condition that did not worsen from baseline is not considered an AE.
d. Results in persistent disability/incapacity

 • The term disability means a substantial disruption of a person's ability to conduct normal life functions. • This definition is not intended to include experiences of relatively minor medical significance such as uncomplicated headache, nausea, vomiting, diarrhea, influenza, and accidental trauma (e.g., sprained ankle) which may interfere with or prevent everyday life functions but do not constitute a substantial disruption.
e. Is a congenital anomaly/birth defect
f. Other situations:

 • Medical or scientific judgment should be exercised in deciding whether SAE reporting is appropriate in other situations such as important medical events that may not be immediately life-threatening or result in death or hospitalization but may jeopardize the participant or may require medical or surgical intervention to prevent one of the other outcomes listed in the above definition. These events should usually be considered serious. • Examples of such events include invasive or malignant cancers, intensive treatment in an emergency room or at home for allergic bronchospasm, blood dyscrasias or

convulsions that do not result in hospitalization, or development of drug dependency or drug abuse.

10.3.3. Recording and Follow-up of AE and/or SAE

AE and SAE Recording

- When an AE/SAE occurs, it is the responsibility of the investigator to review all documentation (e.g., hospital progress notes, laboratory reports, and diagnostics reports) related to the event.
- The investigator will then record all relevant AE/SAE information in the CRF.
- It is **not** acceptable for the investigator to send photocopies of the participant's medical records to sponsor or designee in lieu of completion of the AE/SAE CRF page.
- There may be instances when copies of medical records for certain cases are requested by sponsor or designee. In this case, all participant identifiers, with the exception of the participant number, will be redacted on the copies of the medical records before submission to sponsor or designee.
- The investigator will attempt to establish a diagnosis of the event based on signs, symptoms, and/or other clinical information. Whenever possible, the diagnosis (not the individual signs/symptoms) will be documented as the AE/SAE.

Assessment of Intensity

The investigator will make an assessment of intensity for each AE and SAE reported during the study and assign it to 1 of the following categories:

- Mild: An event that is easily tolerated by the participant, causing minimal discomfort and not interfering with everyday activities.
- Moderate: An event that causes sufficient discomfort and interferes with normal everyday activities.
- Severe: An event that prevents normal everyday activities. An AE that is assessed as severe should not be confused with a SAE. Severe is a category utilized for rating the intensity of an event; and both AEs and SAEs can be assessed as severe.

An event is defined as 'serious' when it meets at least 1 of the predefined outcomes as described in the definition of an SAE, NOT when it is rated as severe.

Assessment of Causality

- The investigator is obligated to assess the relationship between study intervention and each occurrence of each AE/SAE.
- A “reasonable possibility” of a relationship conveys that there are facts, evidence, and/or arguments to suggest a causal relationship, rather than a relationship cannot be ruled out.
- The investigator will use clinical judgment to determine the relationship.
- Alternative causes, such as underlying disease(s), concomitant therapy, and other risk factors, as well as the temporal relationship of the event to study intervention administration will be considered and investigated.
- The investigator will also consult the IB and/or Product Information, for marketed products, in his/her assessment.
- For each AE/SAE, the investigator **must** document in the medical notes that he/she has reviewed the AE/SAE and has provided an assessment of causality.
- There may be situations in which an SAE has occurred and the investigator has minimal information to include in the initial report to sponsor or designee. However, it is very important that the investigator always make an assessment of causality for every event before the initial transmission of the SAE data to sponsor or designee.
- The investigator may change his/her opinion of causality in light of follow-up information and send a SAE follow-up report with the updated causality assessment.
- The causality assessment is one of the criteria used when determining regulatory reporting requirements.

Follow-up of AEs and SAEs

- The investigator is obligated to perform or arrange for the conduct of supplemental measurements and/or evaluations as medically indicated or as requested by sponsor or designee to elucidate the nature and/or causality of the AE or SAE as fully as possible. This may include additional laboratory tests or investigations, histopathological examinations, or consultation with other healthcare professionals.
- If a participant dies during participation in the study or during a recognized follow-up period, the investigator will provide the sponsor or designee with a copy of any post-mortem findings including histopathology.
- New or updated information will be recorded in the originally completed CRF.
- The investigator will submit any updated SAE data to the sponsor or designee within 24 hours of receipt of the information.

10.3.4. Reporting of SAEs**SAE Reporting via Paper CRF**

- Facsimile transmission of the SAE paper CRF is the preferred method to transmit this information to the sponsor or designee.

- Initial notification via telephone does not replace the need for the investigator to complete and sign the SAE report within the designated reporting time frames.
- Contacts for SAE reporting can be found in SAE Report.

10.4. Appendix 4: Contraceptive Guidance and Collection of Pregnancy Information

10.4.1. Definitions

Females of Childbearing Potential

A female is considered fertile following menarche and until becoming postmenopausal unless permanently sterile (see below).

If fertility is unclear (e.g., amenorrhea in adolescents or athletes) and a menstrual cycle cannot be confirmed before first dose of study intervention, additional evaluation should be considered.

Females NOT of Childbearing Potential

Females in the following categories are considered not of childbearing potential:

1. Infertile due to surgical sterilization
 - Documented hysterectomy
 - Documented bilateral oophorectomy
 - Document bilateral tubal ligation
2. Permanent infertility due to an alternate medical cause other than the above, (e.g., mullerian agenesis.)
3. Postmenopausal female defined as either:
 - a woman at least 40 years of age with an intact uterus, not on hormone therapy, who has cessation of menses for at least 12 months without an alternative medical cause, AND a follicle-stimulating hormone >40 mIU/L
 - a woman 55 years or older not on hormone therapy, who has had at least 12 months of spontaneous amenorrhea
 - a woman at least 55 years of age with a diagnosis of menopause prior to starting hormone-replacement therapy.

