5.1. Inclusion Criteria

Participants are eligible to be included in the study only if all of the following criteria apply:

Participant Characteristics

1. Are males or females from 18 to 65 years of age inclusive, at the time of signing the informed consent.
For contraception requirements of this protocol, see Appendix 4 (Section 10.4).
2. Have a body mass index of 19.0 to 35.0 kg/m², inclusive at the time of screening.
3. Are overtly healthy as determined by medical evaluation including:
 - medical history
 - physical examination
 - laboratory tests
 - ECG
 - vital signs.
4. Have clinical laboratory test results within normal reference range for the population or CRU, or results within acceptable deviations that are judged to be not clinically significant by the investigator.
5. Have venous access sufficient to allow for blood sampling as per the protocol.

Informed Consent

6. Capable of giving signed informed consent as described in Appendix 1 (Section 10.1), which includes compliance with the requirements and restrictions listed in the informed consent form (ICF) and in this protocol.

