10.4.2. Contraception Guidance

10.4.2.1. Female Participants

All females must test negative for pregnancy prior to initiation of treatment as indicated by a negative serum pregnancy test at the screening visit followed by a negative urine pregnancy test within 24 hours prior to exposure. A positive urine test will be confirmed with a serum pregnancy test.

Female participants not of childbearing potential are not required to adhere to contraceptive requirements.

Female participants of childbearing potential must agree to use either 1 highly effective method of contraception (<1% failure rate), or a combination of 2 effective methods of contraception, see Section 10.4.3, during the study and until 30 days after the last dose of study medication.

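### The FSH cut-off for postmenopausal status is printed in mIU/L, probably a unit misprint; read literally, it screens out practically no one

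*Protocol*

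**What the plan says.** Protocol 10.4.1 lists three routes by which a woman counts as postmenopausal, and so as not of childbearing potential.

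- **From age 40, with FSH.** This route is for women who still have a uterus, take no hormones and have had no periods for a year. Its closing words are "without an alternative medical cause, AND a follicle-stimulating hormone >40 mIU/L". The laboratory result is an additional condition, joined by a capitalised AND.
- **From age 55, no FSH.** The route covers "a woman 55 years or older not on hormone therapy, who has had at least 12 months of spontaneous amenorrhea".
- **From age 55, no FSH.** The route covers women diagnosed as menopausal before they began hormone replacement.

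The classification has a direct consequence in Protocol 10.4.2.1: "Female participants not of childbearing potential are not required to adhere to contraceptive requirements". Women of childbearing potential must use contraception during the study and for 30 days after the last dose.

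The clinical laboratory table in Protocol 10.2 includes "FSH (postmenopausal females only") as a screening-only test, with no unit and no reference range. The cut-off appears nowhere else in the protocol or SAP, so no other text corrects or explains the unit.

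**The concern.** A cut-off per litre in milli-units is very low for a hormone that, on the reviewer's assumption, is reported in mIU/mL or IU/L. If the printed unit is taken at face value, a woman with a clearly premenopausal FSH meets the condition as easily as a postmenopausal one.

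The list itself shows why the condition is there. From age 55, amenorrhea of 12 months is enough. Below 55 the protocol asks for laboratory confirmation as well. If that confirmation cannot fail, the distinction between the two age groups disappears.

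What is at stake is the contraception exemption, above all for the 30 days after the last dose. Under the Schedule of Activities, pregnancy tests are done at screening (serum) and on Day -1 at admission to the clinical research unit (urine). None is scheduled at the final visit or at early discontinuation, so testing does not cover that window.

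**Working it through.** The cut-off is a stated criterion, not a calculated figure, so there is no plan figure to reproduce. The check is a unit conversion and a comparison.

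**Inputs**

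- Printed cut-off: 40 mIU/L (Protocol 10.4.1).
- Age limits of the routes: 40 with FSH, 55 without (Protocol 10.4.1).
- Enrolment: "Are males or females from 18 to 65 years of age inclusive" (Protocol 5.1), so women aged 40 to 54 can enter.
- FSH in women with functioning ovaries: not in the documents. Assumed to be about 1 to 30 mIU/mL.

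**Step 1: convert the cut-off.** Since 1 L = 1,000 mL and 1 IU = 1,000 mIU, 1 mIU/mL = 1,000 mIU/L = 1 IU/L. Hence 40 mIU/L ÷ 1,000 = 0.04 mIU/mL = 0.04 IU/L.

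**Step 2: compare with assumed values.** Ratio = FSH in mIU/mL × 1,000 ÷ 40.

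| Assumed FSH (mIU/mL = IU/L) | In mIU/L | Ratio to printed cut-off | Meets >40 mIU/L? |
|---|---|---|---|
| 0.03 | 30 | 0.75 | no |
| 0.05 | 50 | 1.25 | yes |
| 0.1 (strongly suppressed) | 100 | 2.5 | yes |
| 1 | 1,000 | 25 | yes |
| 20 | 20,000 | 500 | yes |
| 30 | 30,000 | 750 | yes |

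To fail the criterion as printed, a result would have to be at or below 0.04 IU/L. The conclusion does not depend on the exact range: the whole assumed interval passes, with a margin of at least 25-fold, and even the assumed suppressed value passes.

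**Step 3: see how much hangs on the unit.** The same number per millilitre would be 40 × 1,000 = 40,000 mIU/L, 1,000 times the printed value. On that scale the top of the assumed range, 30 mIU/mL, falls below 40. So every value in the range passes on one reading and none passes on the other. This shows only that the unit decides the classification; it does not establish which reading was meant.

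**Step 4: find who is affected.** A woman of 55 or older who meets the age-40 conditions already qualifies by a route without FSH. The FSH result therefore decides only for ages 40 to 54, in women with an intact uterus, no hormone therapy, and at least 12 months without menses and without another medical cause. The documents give no age or sex distribution, so the number cannot be calculated. It is probably few of about 48 participants.

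**The case against.** The strongest reply is that nothing in the documents contradicts the printed unit. They give no FSH range, assay unit or laboratory limit, so the point needs an outside assumption. That is true, and the assumption is declared. The margin in the table is wide enough that any realistic choice leads to the same place.

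A reader might go further and infer that the FSH confirmation does nothing in practice, or that women will be excused from contraception without it. The documents do not support that. FSH is still drawn at screening, and nothing shows that staff would convert a result by a factor of 1,000 before applying the criterion. A site may simply compare the number its laboratory reports with 40. What is shown is a defect in the written text, not a failure of the safeguard in use. It remains a poor defence of the text that it works only if staff set its unit aside, particularly as Protocol 5 and 8 do not allow waivers.

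Other protections also stand:

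- The woman must still have a year of amenorrhea with no alternative cause and no hormone therapy. Protocol 10.4.1 adds that further evaluation should be considered when fertility is unclear and a menstrual cycle cannot be confirmed.
- The tests do not depend on the classification: "All females must test negative for pregnancy prior to initiation of treatment" (Protocol 10.4.2.1), by serum at screening and by urine within 24 hours before exposure.
- Exclusion criterion 24 removes women planning pregnancy during the study or within 1 month of completing it.
- Participants are resident in the unit from Day -1 to Day 6 of each period, and possibly throughout.

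These limit the effect substantially. They do not replace contraception against an unplanned pregnancy after discharge, which is the part of the concern that remains.

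**Conclusion.** The criterion is wrong as written, most probably through a unit misprint. Read literally, the FSH condition excludes practically no one, and the 40-to-54 group would be judged on unexplained amenorrhea alone.

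The conversion to 0.04 mIU/mL is exact. The statement that practically every woman exceeds it rests on the assumed range of about 1 to 30 mIU/mL. That a misprint is the cause is an inference, since the documents do not state the intended unit.

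The practical impact is small, but the text deserves correction because it is a decision threshold for participant protection and not background description. It should not be read as a threat to the trial's result: FSH enters no endpoint, and the sample size and bioequivalence analysis are unaffected.

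**What to change.** The sponsor's medical lead should verify the intended FSH unit, reconcile Protocol 10.4.1 with the unit the local laboratory reports, and correct the text there. Any eligibility checklist, eCRF edit check or site instruction copied from 10.4.1 should be corrected at the same time. Stating the unit beside the FSH entry in Protocol 10.2 would prevent a repeat. The number and the clinical rule are for the medical lead to confirm; neither is proposed here.

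The cost is a short text correction and no new procedure, because FSH is already measured at screening. If it is made as a protocol amendment, it goes through the ethics submission described in Protocol 10.1.1, so it is sensible to bundle it with other corrections and to tell the site of the clarified unit through the appropriate route.
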